5.1. Objectives

Conducting active post-market surveillance is dynamic. Therefore, the PSR is designed to adapt as technology, information, and/or requirements change with the capability of aggregating multiple surveillance data sources, providing increased value and utility in terms of product performance assessment. The objective of the PSR is to serve as an ongoing source of product performance, patient safety and clinical outcomes information associated with the use of market-released products.

Objectives include:

- To identify device failures, adverse events or adverse event trends

- To characterize patient outcomes
- To characterize patterns of product use
- To characterize predictors of performance and effectiveness
- To identify potential signals for emerging performance issues

6. Design

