Regulatory reporting of Adverse Events will be completed according to local and national law and regulatory requirements. Refer to Table 3 and Table 4 for a list of required site and Medtronic reporting requirements. It is the responsibility of the site to comply with the Adverse Event reporting requirements of their Ethics Board.

All sites are required to follow their local regulatory reporting requirements for market-released products.

Device deficiencies information will be collected throughout the registry and be reported to Medtronic upon site's first awareness. Specific event reporting requirements may be outlined for a given condition, procedure and/or therapy in the Condition/Therapy Appendix.

13. Data Review Committees

A Clinical Event Committee (CEC) may conduct a review of reported events and deaths at regular time intervals, if applicable. The need for CEC review will be determined by Condition/Therapy and the end use of the data (e.g., regulatory reporting, publications, etc.). Use of a CEC will be documented in the associated AP or AD. The CEC is a committee comprised of independent experts with applicable technical and clinical backgrounds.

The committee will be provided with the reporting clinician's assessment of the event and actions taken. The committee is responsible for reviewing the clinician's assessment and adjudicating the event as applicable. If the CEC disagrees with the clinician's assessment, the rationale will be provided to the clinician. Both determinations are retained. The CEC determination will be used for analysis purposes.

14. Statistical Design and Methods

The purpose of the PSR is to better characterize the safety and/or performance of market-released products, therefore sample size calculations serve to ensure sufficient precision for characterization of performance. The exact definition of sufficient precision will vary based on the intended end use of the data and product type. The general concept is that sample sizes should be large enough to generate meaningfully narrow confidence intervals for population parameters of interest. Specific analysis requirements, statistical methods including required effective sample size determinations are defined in the PSR associated AP or AD; refer to Section 6.2.

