Patients may be enrolled prior to or after the surgical or medical procedure. Whether a particular cohort under this CIP enrolls patients before or after surgery or both, is defined in the applicable analysis plan or addendum. The site will make every attempt to approach all eligible patients for enrollment and

Medtronic Business Restricted

perform a thorough review of the patient's medical record to ensure requested baseline and medical history information is complete. When enrolling a patient before surgery, procedures are recommended to occur within 30 days of consent. When enrolling a patient after surgery, it is recommended to do so within 30 days following the procedure. If deemed necessary, the study team is allowed to deviate from those 30 days before or following surgery, provided justification in the applicable analysis plan or addendum.

If the patient is enrolled into the registry prior to the surgical or medical procedure but the procedure is not completed with an eligible product, the patient will be exited from the registry. The data that is to be collected on patients exited early will include the Enrollment CRF and the Exit CRF at minimum. Other CRFs, if collected, will be defined in the applicable analysis plan or addendum. No data will be collected after the patient is exited. Vulnerable patient populations such as pediatric patients may be enrolled when the use of the device is approved in the population and region per the applicable instructions for use (IFU). Regional requirements will be followed and described in the applicable analysis plan or addendum.

Sites may submit to their Ethics Board for a full waiver of consent if applicable. Patients at sites where the Ethics Board *has not* granted a full waiver of consent are considered enrolled once informed consent has been obtained. Patients at sites where the Ethics Board *has* granted a full waiver of consent are considered enrolled once the patient's eligibility is assessed and verified and the Enrollment CRF is complete. Relevant enrollment data collected for eligible patients include but are not limited to:

- Eligibility verification (i.e. Section 8.3 Inclusion Criteria and Section 8.4 Exclusion Criteria).

Study activities (e.g., data collection and entry) can only start after the patient is enrolled in the study.

B.2 Baseline

The following types of data may be collected at baseline for enrolled patients regardless of procedure performed:

- Demographics
- Medical History

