## 5.4 Eligibility

### 5.4.1 Inclusion Criteria

- Subject or legally authorized representative (LAR) provides authorization and/or consent per institution and geographical requirements
- Subject has, or is intended to receive or be treated with, an eligible Medtronic surgical product
- Subject is consented within the enrollment window of the therapy received, as applicable

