### 7.1 Study Subjects

#### 7.1.1 Disposition of Subjects

A subject is enrolled in the study when he/she signs and dates the Informed Consent, unless a full waiver of consent has been approved by the site's IRB or EC, meets all the inclusion/exclusion criteria, and is treated with at least one eligible Medtronic market released surgical product. A flow chart, tables, and/or listings may be used to summarize subjects' disposition.

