#### 7.1.3 Analysis Sets

Subjects included in any analysis sets must consent to the PSR, unless a full waiver of consent has been approved by the site's IRB or EC, and meet all the inclusion/exclusion criteria. They must have been treated with at least one Medtronic market released surgical product. Additional inclusion/exclusion criteria include, but are not limited to specific components or models, time frame, data cutoff date and geography. For details, please refer to Analysis Plan (AP) or Addendum (AD).

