## 7.9.2 Secondary Objective

The secondary objectives are intended to gain additional information about the safety and performance of surgical products. There will be no established performance goals related to the secondary objectives.

All the variables included in the secondary objective will be summarized overall and/or by group if applicable using descriptive statistics. For survival outcomes, Kaplan-Meier method will be used to estimate survival probability. The calculated survival probability at a given time  $t$  is an estimator of survival probability beyond  $t$ , conditional on survival prior to the time  $t$ . The 2-sided point-wise 95% confidence limit will be calculated using the log-log transformation.

Mortality will be calculated. The causes of death and relatedness of death to surgical or medical procedure and/or the product(s) will be summarized in a table. All deaths will be listed.

Device deficiencies (DD) will be summarized by MedDRA terms and product type. All the device deficiencies will be listed.

Product related adverse events will be summarized by MedDRA terms and product type. The number of events and the number and percentage of subjects who experienced the event will be reported.

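### SAP 7.1.3 admits only treated subjects to any analysis set, so a device deficiency that leaves a pre-enrolled patient without any Medtronic surgical product drops out of any deficiency summary run on such a set, which can then be biased low

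*SAP*

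**What the plan says.** SAP 7.1.3 opens with a rule of general scope, "Subjects included in any analysis sets must consent to the PSR" (consent waivers excepted), and adds: "They must have been treated with at least one Medtronic market released surgical product". It lets the Analysis Plan or Addendum add further criteria, but mentions no set that relaxes the treatment condition.

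SAP 7.1.1 goes further and makes treatment part of enrolment: a subject counts as enrolled only if, among other conditions, he or she "is treated with at least one eligible Medtronic market released surgical product". The inclusion criterion in SAP 5.4.1 is wider: "Subject has, or is intended to receive or be treated with, an eligible Medtronic surgical product". Surgical Appendix B.1 allows enrolment before the procedure. It treats the patient as enrolled at consent or, under a full waiver, once eligibility is verified and the Enrollment CRF is complete.

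On deficiencies, Protocol 12.2 says: "Device deficiencies information will be collected throughout the registry and be reported to Medtronic upon site's first awareness". Surgical Appendix B.3 and Table 4 repeat the duty to report on awareness. SAP 7.9.2 then says: "Device deficiencies (DD) will be summarized by MedDRA terms and product type". It also commits to listing every deficiency, but names no population, denominator or rate for them.

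If a procedure is not completed with an eligible product, Surgical Appendix B.1 exits the patient who was enrolled beforehand: "The data that is to be collected on patients exited early will include the Enrollment CRF and the Exit CRF at minimum". Other forms are left to the Analysis Plan or Addendum, and nothing is collected after exit.

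**The concern.** Under a treated-only rule, membership of the analysis set can depend on the outcome being measured. A deficiency needs neither an adverse event nor a completed treatment, since the definition in Protocol Table 2 covers malfunctions and use errors as such. If a device or robotic system fails at set-up and the operation goes ahead with no Medtronic surgical product, a deficiency has occurred but the subject does not meet 7.1.3. The failures most likely to be lost from the summary are the most complete ones.

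This bears on the registry's first listed objective in Protocol 5.1, "To identify device failures, adverse events or adverse event trends", and on device deficiencies as a named secondary outcome in SAP 4.2. The error runs one way: it makes the product look better.

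**Working it through.** **The plan's own figures.** The plan gives no figure for device deficiencies. Its only computed figures are the sample sizes in SAP 6.1. All nine reproduce from N = 1.96² × p(1 − p) / halfwidth², rounded up (for example p = 10%, halfwidth 5%: 138.3, so 139). They do not depend on this point.

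**The rule applied to four patients, all consented before surgery.**

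| Patient | Reportable (Protocol 12.2, Appendix B.3) | In a 7.1.3 set? |
|---|---|---|
| A. Product used, no problem | No deficiency | Yes |
| B. Product used, malfunctions in use | Yes | Yes |
| C. Product fails before use; a replacement unit or another Medtronic surgical product is used | Yes | Yes, on the words of 7.1.3 |
| D. Product fails before use; no Medtronic surgical product is used | Yes | No |

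Only D is lost from the summary. For C with a different, non-eligible Medtronic product, 7.1.3 keeps the subject, whereas 7.1.1 does not regard the subject as enrolled and B.1 exits the subject. The three texts disagree.

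**Direction.** Let D be the proportion of subjects with attempted use who have a deficiency, and f the share of those deficiencies that leave the subject untreated, as for patient D above. Then:

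- rate among all attempts = D
- rate on a treated-only set = D(1 − f) / (1 − Df)

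The second is below the first whenever f > 0 and D < 1, and equal to it at f = 0. Any bias is therefore downward.

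**Size, on assumed inputs.** The documents give neither D nor f.

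| D | f = 0 | f = 0.10 | f = 0.25 | f = 0.50 |
|---|---|---|---|---|
| 2% | 2.00% | 1.80% | 1.51% | 1.01% |
| 5% | 5.00% | 4.52% | 3.80% | 2.56% |
| 10% | 10.00% | 9.09% | 7.69% | 5.26% |

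**Worked example, counts assumed.** There are 200 attempts. Four fail before use with no Medtronic surgical product then used, and 4 deficiencies occur among the 200 − 4 = 196 treated.

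- Treated-only set: 4/196 = 2.0% (exact 95% CI 0.6% to 5.1%)
- Attempted-use set: (4 + 4)/200 = 4.0% (exact 95% CI 1.7% to 7.7%)

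This is D = 4% and f = 0.5 in the formula: 0.04 × 0.5 / (1 − 0.02) = 0.0204.

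**The case against.** The strongest reply is that the record is not lost. A reader might infer that the deficiency removes its own record, and the documents do not support that. A patient enrolled before surgery is in the registry when the product fails. Appendix B.3 and Table 4 require deficiencies to be reported on awareness. B.1 states a minimum set of forms and bars data only after exit, and a failure at the procedure comes before exit. The listing sentence in SAP 7.9.2 carries no population limit, so its plain reading includes patient D. This part of the reply stands, and it confines the point to the summary.

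Second, the SAP defines no deficiency rate or denominator, so it cannot be said that the plan reports 4/196. This also stands. The supportable statement is that a summary or percentage run on a 7.1.3 set can be low, not that a planned estimate is low.

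Third, a reader might take the trigger to be any deficiency that stops the eligible product from being used. That is too wide, because 7.1.3 asks only for some Medtronic market released surgical product. In addition, "treated" is not defined, so a set-up device might be argued to count. That ambiguity is itself a reason to settle the wording.

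Fourth, the Analysis Plan or Addendum could deal with this. It might, but 7.1.3 speaks of criteria to be added to the rule, not of lifting it. SAP 3 also says that an objective covered there will be analysed as the SAP describes. The default should therefore be sound.

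Last, deficiencies are a descriptive secondary outcome with no performance goal. That limits the consequence but does not remove it, given the registry's purpose.

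**Conclusion.** The point holds for the deficiency summary. A stated rule for all analysis sets, with no exception for attempted use, excludes deficiencies that leave a pre-enrolled patient with no Medtronic surgical product. Any resulting bias is downward. Reporting and listing of those deficiencies are not shown to fail.

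The size cannot be found from the documents. It is nil where a replacement or another Medtronic surgical product is used, and nil in cohorts enrolled only after the procedure. Enrolment timing is set per cohort in Analysis Plans or Addenda that are not part of these documents, so how many cohorts are exposed is unknown. The halving from 4.0% to 2.0% in the example follows from assumed counts and should not be read as an estimate for any product.

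The conclusion rests on two readings: that a product opened or set up but not used does not count as treatment, and that the deficiency summary is run on a 7.1.3 set, as the words covering any analysis set imply. The adverse-event rate and the sample-size table are not affected.

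**What to change.** - **SAP 7.1.3:** add a device-deficiency set of all consented (or consent-waived) subjects in whom use of an eligible product was attempted, meaning opened, prepared or set up for the procedure, whether or not treatment followed. Define "treated" in the same place. Keep the treated set for the adverse-event rate.
- **SAP 7.9.2:** run the deficiency summary on the new set, with attempts or subjects with an attempt as the stated denominator. Show deficiencies that prevented use separately. State that the listing is not limited to treated subjects.
- **SAP 7.1.1:** align the enrolment definition with the new set, so that a consented subject with attempted use is not defined out of the study.
- **Surgical Appendix B.1:** cross-refer to the existing reporting duty in B.3, so that a deficiency form is completed before early exit whenever a deficiency occurred.

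The cost is a few sentences of SAP wording, one extra flag to record attempted use, and an existing form for the early exits concerned. The deficiency figure may become slightly less favourable. The change does not reach patients in cohorts enrolled only after the procedure.

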## 7.2 General Methodology

Descriptive summaries, unless otherwise noted, will include the number of subjects (n), mean, standard deviation (SD), minimum, 25th percentile (1st quartile), 50th percentile (median), 75th percentile (3rd quartile), maximum for continuous variables, and the number and percentage for categorical variables. Mean and percentiles will be presented to one more decimal place and SD will be presented to two more decimal places than the significant digits with which the data was collected. Minimum and

---

maximum will be presented to the significant digits with which the data was collected. Percentage will be displayed with one or more decimal places as appropriate. For zero count, no percentage will be presented. Exception may be applied to meet specific requirements.

## 7.2.1 Date format

Format all dates in reports as DD-MMM-YYYY, unless otherwise specified.

## 7.3 Center Pooling

Sites must meet pre-defined criteria to be selected to participate in the registry. The following methods may be incorporated to further minimize potential bias:

- Sites will consider enrollment of all eligible subjects
- Enrollment may be limited at a site level by product and/or by therapy
- Events may be adjudicated by an independent review committee, as determined by therapy or regulatory requirements
- Diverse geographical site representation
- Sites represent various types of practice settings including university, community, public and private
- Data may be assessed by an independent reviewer (e.g., Core lab) as determined by therapy
- Procedures and data collection requirements are standardized

There is no restriction on individual site enrollments as a percent of the total enrollments. However, Medtronic reserves the right to limit or close enrollment at a specific site to minimize potential bias. Data from all the study sites will be pooled for the primary analysis. Descriptive summary may be provided by study site. If substantial center heterogeneity is present, exploratory analysis may be performed to help understand the variation and evaluate the impact on the primary objective.

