10.1 Clinical Data Collection and Procedure Descriptions

Medtronic products may be used to monitor, diagnose and/or treat many medical conditions, therefore the following sections provide a general summary of the type of information gathered and procedures applicable for all PSR enrolled patients regardless of their condition, procedure, and therapy received (Refer to Table 1 for an example).

The PSR is an observational registry intended to collect data consistent with routine clinical care practices. Real-world clinical practice routines are not consistent across sites (i.e., physician preference, patient's condition and/or personal circumstances); therefore, to mitigate potential bias and ensure a robust data set, patient status is required to be reported at regular intervals regardless of whether the patients are seen in-person. Refer to the Condition/Therapy Appendix for more detailed data collection and procedure requirements for a particular patient condition and therapy.

Data collection is intended to reflect routine clinical care procedures and may include prospective and retrospective data. Data collection details and CRFs (where required) are provided under separate cover.

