### 6.1 Sample size determination for event rate

To estimate sample size based on event rate and its pre-defined 95% confidence interval (CI), binomial distribution will be used. Assuming the event rate is  $\hat{p}$ , the sample size,  $N$  is estimated using the following expression (Rosner).

$$N = \frac{1.96^2 \times \hat{p}[1 - \hat{p}]}{(halfwidth)^2}$$

where *halfwidth* is half of the 95% CI width. The table below shows the sample size estimates when the event rate is ranged from 5% to 20% and *halfwidth* is from 5% to 10%.

Event Rate \ Halfwidth	5%	7.5%	10%
5%	73	-	-
10%	139	62	-
15%	196	88	49
20%	246	110	62

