#### 7.9.1.3 Analysis Method

Event rate is calculated as number of events divided by number of units (e.g. subjects or product uses) where events are evaluated among subjects who have enrolled, met all the inclusion/exclusion criteria, and underwent surgical procedure. If there are more than one event per unit, only the first event is relevant to the primary objective.

Two-sided 95% confidence interval (CI) of the event rate will be calculated using Binomial distribution. All the events will be summarized in a table by Medical Dictionary for Regulatory Affairs (MedDRA)

terms. The number of events, and the number and percentage of subjects who experienced the event will be reported. Surgical or medical procedure related events and/or the product related events will be listed.

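### The pooled binomial 95% CI carries no allowance for between-site variation, so with few or large sites it can cover less than 95% for the worldwide rate that the SAP claims to estimate

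*SAP*

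**What the plan says.** The sample size rests on independent subjects. SAP 6.1: "To estimate sample size based on event rate and its pre-defined 95% confidence interval (CI), binomial distribution will be used". The formula there has no design effect, and its table runs over event rates of 5% to 20% and half-widths of 5% to 10%.

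The analysis follows the same model. SAP 7.3: "Data from all the study sites will be pooled for the primary analysis". SAP 7.9.1.3: "Two-sided 95% confidence interval (CI) of the event rate will be calculated using Binomial distribution". The type of binomial interval (exact, Wald or other) is not named.

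On differences between sites, SAP 7.3 offers a by-site descriptive summary, which is optional, and this: "If substantial center heterogeneity is present, exploratory analysis may be performed to help understand the variation and evaluate the impact on the primary objective". It sets no threshold for substantial heterogeneity and no method. On site size the same section says: "There is no restriction on individual site enrollments as a percent of the total enrollments". The sponsor keeps the right to limit or close a site, and Protocol section 14 mentions 15% of projected enrollment as an optional guideline for closing a product at a site.

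SAP 6.2 states the target of inference: the enrolled sample is taken to represent the worldwide population, and the estimates to represent worldwide performance.

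**The concern.** With a worldwide target, the sites in a cohort are a sample of the places where the product is used. The uncertainty of the estimate then includes the variation between sites, and a binomial interval on pooled data leaves that part out.

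The documents give reasons to expect some variation. Practice settings are deliberately diverse. Whether a complication is reported depends partly on what the investigator regards as normal for the procedure (Surgical Appendix, Table 1). Relatedness is the clinician's assessment (Protocol 12.2), and every category from possible upwards counts as related (SAP 7.9.1.2). Committee adjudication is optional (Protocol 13).

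The primary objective has no hypothesis, so the estimate and its CI are its main statistical result. If that interval covers less than its nominal 95%, reports will state the worldwide rate with more certainty than the data support.

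**Working it through.** **1. The plan's own figures.** N = 1.96² × p(1−p) / h², rounded up. For p = 20% and h = 5%: 3.8416 × 0.16 / 0.0025 = 245.86, so 246, as in the table. For p = 10% and h = 5%: 138.30, so 139. All nine cells of the SAP 6.1 table reproduce. The table is right under independence.

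**2. Inputs that the documents do not give.** Neither ICC nor number of sites appears, so both are assumed: ICC 0.01, 0.02 and 0.05, with 7, 12 or 50 sites of about equal size. Twelve sites at N=246 means 20.5 subjects per site, about 8% of the total. Seven sites means 35.1 per site, about 14%. Both stay inside the protocol's 15% guideline, which if applied requires at least seven sites (1/0.15 = 6.7).

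**3. Design effect.** DE = 1 + (m−1) × ICC, where m is the site size. The half-width that would be needed for the worldwide rate is about 5.0 × √DE points (p = 20%, N = 246).

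| Sites | m | ICC | DE | Half-width needed (points) |
|---|---|---|---|---|
| 12 | 20.5 | 0.01 | 1.195 | 5.5 |
| 12 | 20.5 | 0.02 | 1.390 | 5.9 |
| 12 | 20.5 | 0.05 | 1.975 | 7.0 |
| 7 | 35.1 | 0.01 | 1.341 | 5.8 |
| 7 | 35.1 | 0.02 | 1.683 | 6.5 |
| 7 | 35.1 | 0.05 | 2.707 | 8.2 |
| 50 | 4.9 | 0.02 | 1.078 | 5.2 |

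**4. Coverage.** Site rates were drawn from a beta distribution with the stated ICC, and the pooled interval was checked against the overall rate of 20% (N = 246).

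| Sites | Interval | ICC 0.01 | ICC 0.02 | ICC 0.05 |
|---|---|---|---|---|
| 12 | exact (Clopper-Pearson) | 94% | 92% | 86% |
| 7 | exact (Clopper-Pearson) | 93% | 89% | 79% |
| 7 | Wald | 90% | 85% | 75% |
| about 50 (5 per site) | exact (Clopper-Pearson) | 96% | 95% | 94% |

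The mean width of the exact interval hardly moves: its half-width is 5.1 to 5.2 points at every ICC tried. The loss is in coverage.

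**5. A smaller cohort.** At p = 10%, N = 139 and 7 sites, exact coverage is 95.1%, 93.3% and 87.9% at the same three ICCs. At ICC 0.01 the exact interval's own conservatism (96.7% at ICC 0) absorbs the site effect.

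**6. A different target.** If inference is confined to the sites that actually enrolled, the same exact interval covers about 96% at p = 20%, N = 246 and 7 sites for all three ICCs. The problem therefore depends on the worldwide claim in SAP 6.2.

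**The case against.** The case on the other side has four parts.

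- **This is an umbrella SAP.** The number of sites and the sample size belong to each Analysis Plan or Addendum, and a study-specific SAP addendum may add analyses. That stands, and it is why the size of the effect cannot be fixed here. But no text requires an addendum to deal with sites, and SAP section 3 says that an objective covered by this SAP is analysed as the SAP describes.
- **Heterogeneity is addressed.** Site summaries, the exploratory analysis, the right to close a site, the 15% guideline and the search for outlier sites (Protocol 16.1) are real provisions. The first four are optional, and none of the five changes the primary interval.
- **No decision hangs on the interval.** There is no hypothesis, so no pass or fail turns on its coverage. This limits the consequence but does not make the stated precision right.
- **The remedy can be worse than the fault.** Robust intervals are unreliable with few sites or few events. At N = 73, p = 5%, 7 sites and ICC 0.02, one covers about 86%, against 95% for the exact interval. This stands and limits the fix.

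A reader might also infer more than the documents support:

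- *That any between-site variation makes the interval too narrow.* It does not: there is no effect at one subject per site, and 50 sites at ICC 0.02 leave exact coverage at 95.5%.
- *That the printed intervals will miss the half-widths in 6.1 because of sites.* They will stay near plan, at about 5.2 points against 5.0, and that small excess comes from using an exact interval.
- *That Protocol 10.1 shows event rates to differ by site.* Its statement "Real-world clinical practice routines are not consistent across sites" concerns care routines and justifies status reports at regular intervals. It makes variation plausible but does not measure it.
- *That the SAP expects substantial heterogeneity.* The wording in 7.3 is conditional.

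**Conclusion.** The point holds in a limited form. The sample size and the primary interval both assume independent subjects, no site-adjusted interval is specified, and the claim to worldwide performance makes between-site variance part of the uncertainty. At N = 246 and a 20% rate, the shortfall in exact coverage is about 1 to 9 points with 12 sites and 2 to 16 points with 7 sites over ICC 0.01 to 0.05. It is larger for a Wald interval and negligible with many small sites. These figures rest on assumed ICCs, equal site sizes and a beta-binomial model. The gap is correctable and does not invalidate the registry, but it should be closed before cohorts with few or large sites are reported.

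**What to change.** 1. In SAP 7.9.1.3, keep the binomial CI as primary and name it as exact (Clopper-Pearson).
2. In the same section, prespecify a site-clustered 95% CI as a supportive analysis. Candidates are a beta-binomial model, or a robust variance by site with a small-sample correction and a t reference. State the scale (proportion or logit) on which it is formed.
3. Set in advance, in the SAP or in each Analysis Plan or Addendum, the minimum number of sites and events for reporting it. Below that, report the exact CI alone.
4. Do not choose between the two intervals after seeing them. If the clustered CI is materially wider, the report should say that the binomial CI understates uncertainty for worldwide inference.
5. In SAP 6.1, add that the tabulated half-widths assume no between-site variation.

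The cost is a few sentences of SAP text and some programming, with no new data, since each subject's site is known. The downside is a somewhat wider supportive interval, which is unreliable with few sites or few events.
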